6.6.1 Dose modification criteria

6.6.1.1 General guidelines for adagrasib (Part-3)

The following are the general guidelines for withholding, resumption or re-challenge of treatment with adagrasib:

- following adagrasib dose reduction and control of an AE, re-challenge at a higher adagrasib dose may be permitted after discussion with the Sponsor;

- if resumption of dosing for adagrasib is delayed for ≥ 14 days due to an AE that is at least suspected to be attributable to study treatment, then resumption at a reduced dose should be considered;
- if treatment with adagrasib is withheld for ≥ 22 consecutive days, then permanent discontinuation from treatment with one or both agents should be considered; and
- if a treatment-related AE recurs despite dose reduction of adagrasib to the lowest dose anticipated, then permanent discontinuation from study treatment should be considered, unless after discussion with the Sponsor it is considered to be in the best interest of the participant to continue.

Treatment interruptions and modification guidelines are provided in Appendix 9 ([Section 10.9](#)).

Additional guidelines for adagrasib:

Hepatic Toxicities

Hepatic toxicities that are considered to be causally related to adagrasib should initially be managed with treatment interruption of one or both study drugs as outlined in [Table 27](#). Evaluations for confounding factors (eg, cholestasis, metastasis, or viral infection) should be performed as clinically indicated, and more frequent monitoring of a hepatic panel (including AST, ALT, alkaline phosphatase, and bilirubin) should be considered for those participants with transaminase increases. Following resolution of toxicity to the specified degree, dose reduction of adagrasib should be implemented.

Other Laboratory Investigation-Based Toxicities

Other laboratory investigation-based toxicities that are considered to be causally related to adagrasib should initially be managed with treatment interruption of adagrasib as outlined in [Table 27](#). Following resolution of toxicity to the specified degree, dose reduction of adagrasib should be implemented.

Cardiac Toxicities

Cardiac toxicities that are considered to be causally related to adagrasib should initially be managed with treatment interruption of adagrasib as outlined in [Table 27](#). Cardiology consultation should be obtained for cases of QTcF prolongation or LVEF decreases falling into the categories indicated in [Table 27](#). In addition, more frequent monitoring of electrolytes that include potassium and magnesium should be considered for participants with vomiting, diarrhea, or past instances of hypokalemia or hypomagnesemia that could recur, and oral and/or intravenous supplementation should be considered for levels below the lower limit of normal. Additionally, arrhythmia should be included in the differential diagnosis of relevant AEs (eg, palpitations, syncope, pre-syncope, or unexplained dyspnea), and unscheduled ECGs should be performed for participants with such events or electrolyte abnormalities as clinically indicated. Additional assessments of LVEF should be performed as clinically indicated at the Investigator's discretion if there are signs or symptoms of cardiotoxicity.

Following resolution of toxicity to the specified degree, dose reduction of adagrasib should be implemented.

Pneumonitis

Pneumonitis has been reported in the Phase 1 study of adagrasib. An evaluation should be performed to assess the attribution of pneumonitis to adagrasib. Pneumonitis considered to be causally related to adagrasib should be initially managed with treatment interruption of adagrasib as outlined in [Table 27](#). Following resolution of toxicity to the specified degree, dose reduction of adagrasib should be implemented.

Other Toxicities

Other toxicities that are considered to be causally related to adagrasib should initially be managed with treatment interruption as outlined in [Table 27](#). Following resolution of toxicity to the specified degree, dose reduction of adagrasib should be implemented.

Hormonal Contraceptives and Thrombotic Events

In female participants using hormonal contraceptives, the potential exists for adagrasib to inhibit hepatic cytochrome P450 and CYP3A4 and increase exposure to hormonal contraceptive levels, with the associated risk of venous thromboembolism (e.g., deep vein thrombosis or pulmonary embolism). Precautions should be taken in participants with recent, clinically significant thrombotic events, and all participants using hormonal contraceptives should be closely monitored for emerging signs of thrombotic events. Treatment with adagrasib should be interrupted in participants with signs or symptoms of thrombosis and permanently discontinued in participants who develop clinically significant thromboembolic complications. If in the judgment of the Investigator resumption of treatment with adagrasib is in the best interest of the participant, concomitant treatment with hormonal contraceptives should be discontinued.

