Skin reactions	
Grade 1 or 2 (tolerable): Administer supportive care and continue study drugs
 
Intolerable Grade 2-Grade 3: Hold both drugs until < Grade 2. If improves to < Grade 2 within 4 weeks, then reduce SAR442720 by one dose level and resume combination drugs at the same dose level.
 
Suspected Stevens-Johnson Syndrome (SJS) or toxic epidermal necrolysis (TEN): Withhold both drugs until adverse reactions recover to Grade 0-1.
 
Grade 4: Hold both drugs until < Grade 1. If improves to < Grade 1 within 4 weeks, resume, reduce SAR442720 by two dose levels and resume combination drugs at the same dose level.
 
Grade 4 or confirmed SJS or TEN: Permanently discontinue both drugs
 
If \geq Grade 3 rash recurs despite two SAR442720 dose level reductions, permanently discontinue both drugs.
 
If rash does not improve within 4 weeks, permanently discontinue both drugs.

Ocular symptoms > Grade 2	
Hold both study drugs and obtain ophthalmology consult.
 
RVO: Any grade, permanently discontinue both drugs (Part-1, 2, and 4 only). In Part-3 permanently discontinue SAR442720 but may continue adagrasib, please consult with the Medical Monitor.
 
Neurosensory retinal detachment: Hold both drugs until resolution to \leq Grade 1. If resolves within 4 weeks, then reduce SAR442720 by one dose level. If visual symptoms > Grade 2 recur despite two dose level reductions, permanently discontinue both drugs. (Part-1, 2 and 4 only). In Part-3 permanently discontinue SAR442720 but may continue adagrasib, please consult with the Medical Monitor.
 
Uveitis/iritis > Grade 2: Hold both study drugs. If resolves to \leq Grade 1 within 4 weeks, then reduce SAR442720 dose by one level and resume both study drugs. If recurs despite two dose level reductions of SAR442720, permanently discontinue both drugs. If > Grade 1 symptoms recur or follow-up ophthalmology examination results worsen, withhold treatment (either SAR442720 and pembrolizumab or SAR442720 and adagrasib) and either further decrease dose or permanently discontinue treatment.
 
Other > Grade 2 AE: Hold SAR442720. If AE doesn't improve within 2 weeks, then consider holding the combination drug. If no improvement within 4 weeks from onset, consider permanently discontinuing both drugs. In ambiguous cases, please consult with the Medical Monitor.

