Hemorrhage > Grade 3	
Rule out other causes.
 
Grade 3: Hold both study drugs until resolution to \leq Grade 1. If hemorrhage is associated with thrombocytopenia or reduced platelet count from baseline hold both drugs. In Part-1, 2, and 4, if resolves within 4 weeks, consider restarting SAR442720 at a lower dose and restarting pembrolizumab at same dose (dose reduction is not allowed for pembrolizumab). In Part-3, if resolves within 4 weeks, consider restarting SAR442720 and adagrasib at a lower dose. In ambiguous cases, please consult with the Medical Monitor.
 
Grade 4 or CNS hemorrhage: permanently discontinue both drugs.

Diarrhea and other GI toxicities	
Grade 1-2 Diarrhea: Maximal supportive care. Continue both drugs at current doses.
 
Grade \geq3 Diarrhea: Hold both study drugs (if receiving maximal supportive care) until \leqGrade 1. If improves within 4 weeks, then dose reduce SAR442720 and adagrasib (in Part-3), and start pembrolizumab at same dose (in Part1, 2 and 4); if diarrhea is not resolved to \leq Grade 1 within 4 weeks, permanently discontinue both drugs.
 
Grade 3 Nausea >72 hours despite therapy; hold both drugs until \leq Grade 1 or return to baseline, dose reduce SAR442720 and adagrasib (in Part-3),
 
Grade \geq3 Pancreatitis, permanently discontinue both drugs.
 
Asymptomatic Grade 3 Amylase or Lipase Elevation >8 days, hold until \leq Grade 1 or return to baseline, resume both drugs at same dose.

AE	Action
Colitis	
Grade 2 or 3: Withhold both study drugs until adverse reactions recover to Grades 0 to 1.
 
Grade 4 or recurrent Grade 3: Permanently discontinue both study drugs.
 
Please consult Medical Monitor for ambiguous cases.

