Hematologic lab abnormalities > Grade 3	
Assess for other causes. Hold concomitant medications associated with myelosuppression.
 
Grade 3 neutropenia, thrombocytopenia: Hold both drugs if clinically indicated until $<$ Grade 1 or baseline. If improves within 4 weeks, restart pembrolizumab or adagrasib at same dose and administer SAR442720 one dose level lower. If does not improve within 4 weeks, discontinue both drugs.
 
Grade 3 febrile neutropenia: Hold both drugs until fever resolves and ANC $<$ Grade 1 or baseline. If improves within 2 weeks, restart pembrolizumab at same dose and SAR442720 and adagrasib 1 dose level lower. If does not improve within 2 weeks, discontinue both drugs.
 
Grade 3 anemia: Assess transfusion history. Transfuse per institutional guidelines. Continue pembrolizumab, and hold SAR442720 if clinically indicated until $<$ Grade 1. If improves within 4 weeks, restart SAR442720 one dose level lower. If does not improve within 4 weeks, consider discontinuation of both drugs. Hold adagrasib until \leq Grade 1 or baseline and may resume at the same dose level.
 
Grade 4 cytopenias: Hold both drugs until resolves to $<$ Grade 1 or baseline. If improves within 4 weeks, restart both drugs; reduce both SAR442720 and adagrasib one dose level lower (pembrolizumab dose reduction is not allowed). If does not improve within 4 weeks, discontinue both drugs.
 
Thrombocytopenia associated with clinically significant bleeding, at any level: Hold both drugs and follow hemorrhage recommendations.
 
Uncomplicated Thrombocytopenia (without clinically significant bleeding):
 
Grade 1 to 2: Continue treatment at current dose level and frequency and monitor closely
 
Grade 3 to 4: Manage per institution guidelines and interrupt dosing of both study drugs until participant recovers to Grade 1 or better. If recovery occurs, the investigator may resume dosing both study drugs at the same dose level and frequency, if clinically appropriate. If Grade 3 to 4 events recur again, hold dose until recovery to Grade 1 or better and consider re-introducing study drug at reduced frequency, or withdrawing participant from study therapy.
 
Please contact Medical Monitor for ambiguous cases.

AE	Action

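### Table 27 gives two incompatible instructions for Grade 4 skin reactions; for adagrasib, it does not say that Section 6.6.1.1 overrides a same-dose restart, and no dose below 400 mg BID is defined

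*Protocol*

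**What the plan says.** **Grade 4 skin reactions (Appendix 9, Table 27, skin reactions row).** After improvement to below Grade 1 within 4 weeks, the row says: "resume, reduce SAR442720 by two dose levels and resume combination drugs at the same dose level". A later line in the same cell calls for permanent discontinuation of both drugs at Grade 4, or for confirmed Stevens-Johnson syndrome (SJS) or toxic epidermal necrolysis (TEN). The row is not limited to any Part. Table 26, the general guidance, also gives permanent discontinuation at Grade 4.

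**Adagrasib after an attributed event (Section 6.6.1.1).** Under a sub-heading for additional adagrasib guidelines, the section sets a rule for events causally related to adagrasib. For the residual category it reads: "Other toxicities that are considered to be causally related to adagrasib should initially be managed with treatment interruption as outlined in" Table 27, and then: "Following resolution of toxicity to the specified degree, dose reduction of adagrasib should be implemented". The same closing sentence follows the hepatic, other laboratory, cardiac and pneumonitis paragraphs.

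**Adagrasib restart in Table 27.**
- Intolerable Grade 2 to Grade 3 skin reactions: "then reduce SAR442720 by one dose level and resume combination drugs at the same dose level".
- Grade 3 neutropenia or thrombocytopenia, if drugs were held and the event improves within 4 weeks: "restart pembrolizumab or adagrasib at same dose and administer SAR442720 one dose level lower".
- Asymptomatic Grade 3 amylase or lipase elevation beyond 8 days: hold to "Grade 1 or return to baseline, resume both drugs at same dose".
- Uncomplicated Grade 3 to 4 thrombocytopenia: "If recovery occurs, the investigator may resume dosing both study drugs at the same dose level and frequency, if clinically appropriate".

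**Adagrasib doses.** Protocol Tables 14 and 17 and SAP Section 1.1 list only 400 mg BID and 600 mg BID. Section 6.6 describes a Part-3 reduction step for SAR442720 only. Section 6.6.1.1 links consideration of permanent discontinuation to recurrence at the lowest anticipated adagrasib dose, without giving that dose in mg.

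**The concern.** Dose-modification text should lead two sites with the same patient to the same dose. Here it may not, in three places. After a Grade 4 rash, one site could re-expose the participant and another stop treatment, each following the cell. After Grade 3 neutropenia or an intolerable rash attributed to adagrasib, one site could restart at the full dose under Table 27 and another reduce under Section 6.6.1.1. When a reduction is due at 400 mg BID, a site has to invent a dose, leave the dose unchanged, or stop. The first is a participant-safety matter in every Part. The other two affect how uniformly adagrasib is dosed in Part-3, and so what the tolerability and response data describe.

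**Working it through.** The documents give no figure to reproduce. The check sets the instructions side by side.

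**Step 1. Grade 4 skin reaction.** Take a Grade 4 rash that is not SJS or TEN and that improves to below Grade 1 within 4 weeks. The conditions of both lines are met. The restart line gives SAR442720 two levels lower and the combination drug unchanged. The discontinuation line gives neither drug. Nothing in the cell ranks them. The Appendix 9 rule to follow the most conservative advice covers several adverse events in one participant, not two instructions for one event. Table 26 agrees with stopping. That is support rather than proof, because Table 27 departs from Table 26 elsewhere: it allows restarts after Grade 4 cytopenias and, in Parts 1, 2 and 4, after Grade 4 liver abnormalities.

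**Step 2. Same-dose restart against the attribution rule.**

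| Event | Table 27: adagrasib restart | If attributed, Section 6.6.1.1 | Reading |
|---|---|---|---|
| Intolerable Grade 2 to Grade 3 skin | Same dose, directed | Reduce | Precedence unstated |
| Grade 3 neutropenia, when held | Same dose, directed | Reduce | Precedence unstated |
| Asymptomatic Grade 3 amylase/lipase, >8 days | Same dose, directed; but the other non-hematologic row directs a lower dose for clearly attributed Grade ≥3 non-hematological laboratory abnormalities | Reduce | Tension inside Table 27 |
| Grade 3 anemia; uncomplicated Grade 3 to 4 thrombocytopenia | Same dose, permitted | Reduce | Not counted |
| Grade ≥3 creatinine, ≤22 days | Same or one level lower, permitted | Reduce | Not counted |

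Thrombocytopenia is named with neutropenia in the directed line, but the permissive and hemorrhage lines also cover it, so only neutropenia is counted. That leaves two lines.

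Dose difference at 600 mg BID:
- same dose: 2 × 600 = 1200 mg/day
- one level lower: 2 × 400 = 800 mg/day
- change: (800 − 1200)/1200 = −33%

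**Step 3. The adagrasib ladder.** By Table 14, adagrasib is 400 mg BID at DL(-)1, DL1, DL2 and DL3b, and 600 mg BID at DL3a and DL4. So 4 of 6 levels are already at the lowest listed dose, and even DL(-)1 lowers only SAR442720.
- From 600 mg BID, one level lower is 400 mg BID. Two levels lower, an option in the Part-3 QTcF line, is undefined.
- From 400 mg BID, one level lower is undefined.

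At least eight Table 27 lines direct an adagrasib reduction in Part-3:
1. Grade ≥3 diarrhea
2. Grade 3 nausea beyond 72 hours
3. Grade 2 liver abnormality
4. Grade 3 liver abnormality
5. Grade ≥3 QTcF prolongation
6. Grade 3 febrile neutropenia
7. Grade 4 cytopenias
8. Intolerable Grade 2 or Grade 3 other non-hematologic events

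In the escalation cohorts, Section 6.6 bars reductions in Cycle 1 unless a DLT has occurred, so there the gap mostly arises later.

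**The case against.** The strongest reply is that Section 6.6.1.1 and Table 27 do not conflict at all. The section refers first to Appendix 9 and then adds guidelines limited to events causally related to adagrasib. In ordinary drafting that is an overlay: Table 27 applies by default, and the attribution rule takes over when adagrasib is blamed. This largely stands, and it is why step 2 is a precedence gap and not a contradiction. What remains is that Table 27, which sites will have in hand, does not say so, and that the pointer to Table 27 in Section 6.6.1.1 attaches to the interruption and not to the restart dose.

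Appendix 9 is also expressly guidance subject to clinical judgment, and the hematologic row adds: "Please contact Medical Monitor for ambiguous cases". That limits the consequences. It does not tell a site which of two Grade 4 skin lines to apply, nor supply a dose the protocol never lists.

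On the ladder, one can fairly answer that 400 mg BID is evidently the floor, since nothing lower appears, and that one level down from 600 mg BID works. Both points stand. The remaining gap is what to do when a reduction is triggered at 400 mg BID or when two levels are chosen from 600 mg BID.

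Three stronger inferences are tempting but not supported:
- **The amylase/lipase line is a third clean conflict with Section 6.6.1.1.** It is not, because Table 27 itself directs a lower dose once such an abnormality is clearly attributed.
- **The adverse-event rates in Section 2.3.1.4 size the problem.** They cover all grades and pool monotherapy with combinations, while most triggers are Grade 3 or higher. They do not bound Part-3 rates either, since Section 2.3.1.5 expects that overlapping gastrointestinal toxicity may be more frequent with this combination.
- **A reduction due at 400 mg BID means adagrasib must stop.** Section 6.6.1.1 asks only that discontinuation be considered, even after recurrence at the lowest dose, and allows continuation after discussion with the Sponsor. A mandatory stop would also end adagrasib for a Grade 2 liver abnormality at the starting dose.

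**Conclusion.** The point holds in three parts of unequal weight. The Grade 4 skin cell is wrong as written: two instructions cannot both be followed, and this reaches all Parts. The relation between Section 6.6.1.1 and Table 27 is unclear for two lines, Grade 3 neutropenia when drugs are held and intolerable Grade 2 to Grade 3 skin reactions. It matters only when the event is attributed to adagrasib, and at 600 mg BID the difference is one level (−33%). The adagrasib ladder has no defined step below 400 mg BID, the dose at four of six planned levels, although at least eight Table 27 lines direct a reduction.

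The number of participants affected cannot be stated. The documents give neither the Part-3 RP2D nor grade-specific rates for the combination. The conclusion rests on the current protocol text and assumes that the phrase combination drugs in Table 27 means adagrasib in Part-3, as the table's title indicates.

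**What to change.** 1. **Skin reactions row, Table 27.** Delete the Grade 4 restart line and keep permanent discontinuation. The cost is that a participant with a Grade 4 rash that is not SJS or TEN loses the option to restart. If the clinical team wants that option, the discontinuation line must be limited to SJS and TEN instead.
2. **One general note to Table 27.** For example: for events judged causally related to adagrasib, the reduction in Section 6.6.1.1 applies over any same-dose restart line. This settles the two lines and the amylase/lipase tension together. It would also override the permissive same-dose options for anemia, thrombocytopenia and creatinine when the event is attributed. If those should stay, the note must exempt them.
3. **Section 6.6.1.1.** Replace the undefined lowest dose with the lowest permitted dose: 400 mg BID, unless the clinical team names a lower one. State what happens when a reduction is triggered there, or when two levels are chosen from 600 mg BID. Keep the present wording that discontinuation is considered and may be discussed with the Sponsor. Whether to add a lower level is a clinical decision that the documents do not settle.

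The cost is one deletion, one note and one or two sentences, with no new data, visits or analyses. Because items 1 and 3 affect treatment, they belong in the next amendment and need the ethics approval that protocol Section 10.1.1 requires.

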6.6.1.2 Management of diarrhea

Evaluate for other or concomitant causes, including medications (eg, stool softeners, laxatives, antacids), infection including *Clostridium difficile*, malabsorption/lactose intolerance, fecal impaction, and dietary supplements high in fiber.

For Grade 1 or 2 diarrhea, dietary modifications should be considered including cessation of lactose-containing products, eat small meals, and adequate hydration. Consumption of the BRAT (banana, rice, apples, toast) diet may be helpful. In addition, loperamide or diphenoxylate/atropine, or codeine may be used or alternatives in refractory cases such as octreotide and budesonide.

For > Grade 2 diarrhea, consider hospitalization for fluid and electrolyte replacement and antibiotics, particularly if accompanied by fever or Grade 3 to 4 neutropenia.

Please refer to [Table 27](#) for dose modifications guidelines. For immune related colitis, defer to institutional guidelines.

Consultation with a gastroenterologist should be considered, particularly for severe or refractory cases.

6.6.1.3 Management of ophthalmologic complications

The causal relationship between a change in vision and the study treatment should be carefully explored and an ophthalmologist should be consulted. Immediate consultation should be sought for Grade >1 visual changes. Special attention should be given to retinal (eg, central serous retinopathy [CSR]) or retinal vein abnormalities (eg, RVO). If consultation cannot be obtained within 7 days of onset, interrupt treatment (either SAR442720 and pembrolizumab or SAR442720 and adagrasib) until the consultation has occurred.

If RVO is diagnosed, permanently discontinue treatment (either SAR442720 and pembrolizumab or SAR442720 and adagrasib) immediately and treat per institutional guidelines. If uveitis is diagnosed, withhold treatment (either SAR442720 and pembrolizumab or SAR442720 and adagrasib) and consider use of topical steroids until resolution. If CSR or neurosensory retinal detachment is diagnosed, withhold treatment until symptoms resolve and retinal exam shows resolution. Restart medication(s) at one dose level lower and close monitoring following re-initiation of medication(s). If > Grade 1 symptoms recur or follow-up ophthalmology examination worsens, withhold treatment (either SAR442720 and pembrolizumab or SAR442720 and adagrasib) and either further decrease the dose or permanently discontinue treatment.

